|  | 
abnormalities on Day 1;
 

• Change in SBP and DBP from baseline up to EOS;

• Change in FEV1 and FVC, expressed in absolute value (L) and percent value from baseline up to EOS;

• Occurrence of treatment-emergent decrease of FEV1 or FVC > 15% from baseline values;

• Change in laboratory parameters (hematology, blood chemistry, and urinalysis) from baseline up to EOS;

• Treatment-emergent laboratory abnormalities according to CTCAE 2010 v4.03 [CTCAE 2010] and Food and Drug Administration (FDA) guidelines [FDA 2009] (for ALT/AST/TBL);

• Change in protein-to-creatinine ratio from baseline to EOT;

• Change in body weight from baseline to EOT.

 
#AESI considered for the analyses are described in Appendix 3.
 
Pharmacokinetic endpoints
 

• Ctrough ACT-33441 plasma concentrations prior to dosing at Weeks 2, 4, 8, and 12 (EOT) or at EOT visit after premature study treatment discontinuation (if applicable);

• ACT-33441 plasma concentration at EOS (i.e., 6 weeks after study treatment discontinuation).

 
Exploratory disease activity endpoints
 

• Change in SLEDAI-2K score from baseline to each post-baseline assessment;

• Change in Physician's Global Assessment (PGA) score from baseline to each post-baseline assessment;

• Change in SLEDAI-2K mucocutaneous and/or muscoskeletal scorings from baseline to each post-baseline assessment.

 
Quality of life endpoints
 

• Change in SF-36v2TM Health Survey domain and

 |
|--|--|

|                         |  |
|-------------------------|--|
|                         | 
component scores from baseline to EOT.
 
Exploratory biomarker endpoints
 

• Change in immunoglobulin serum levels (IgG, IgM, IgA) from baseline to each post-baseline assessment;

• Change in ANA and anti-dsDNA antibody titers from baseline to each post-baseline assessment;

• Change in serum complement components C3 and C4, C-reactive protein, fibrinogen, B lymphocyte stimulator and C-X-C motif chemokine 10 from baseline to each post-baseline assessment;

• Change in blood lymphocyte subsets from baseline to EOT and EOS.

  |
| ASSESSMENTS             | Refer to the schedule of assessments in Table 1.   |
| STATISTICAL METHODOLOGY | 
All statistical analyses will be conducted by Actelion or by designated Contract Research Organizations supervised by Actelion.
 
The SAP will be finalized prior to database lock.
 
Baseline is defined as the last assessment prior to initiation of the study treatment.
 
Analysis sets
 
Screened Analysis Set: includes all subjects who were screened and received a subject number.
 
Safety Analysis Set: includes all randomized subjects who received at least one dose of study treatment. Unless otherwise stated, any analysis using the Safety Analysis Set will use all available safety data up to 6 weeks after discontinuation of study treatment. Subjects will be analyzed based on actual dose taken, not the randomized dose.
 
PD Analysis Set: includes all subjects who received at least 3 weeks of study treatment and have at least one lymphocyte count measurement between the Week 4 visit and Week 12 visit. Subjects will be analyzed according to the treatment they received.
 
Full Analysis Set (FAS): includes all randomized subjects. Subjects will be analyzed according to their randomized
 |

|  |   |
|--|---|
|  | 
treatment.
 
Per-Protocol Set (PPS): defined as subjects from the FAS without any major protocol deviations. Major protocol deviations are described in Section 11.2.4.
 
PK Analysis Set: includes all randomized subjects who received at least one ACT-334441 dose and provided at least one blood sample for PK evaluation. Subjects will be analyzed based on actual dose taken, not the randomized dose.
 
Pharmacodynamic variable
 
The change in lymphocyte count from baseline to EOT is defined as:
 

• Total lymphocyte count at EOT – total lymphocyte count at baseline

 
Last observation carried forward (LOCF; using the Week 4 visit or later) will be used for subjects with a missing EOT assessment.
 
Exploratory disease activity variables
 
The change from baseline in the SLEDAI-2K (modified to exclude leukopenia) score at each visit is calculated as :
 

• SLEDAI-2K score at each visit – SLEDAI-2K score at baseline.

 
The change from baseline in PGA score and the SLEDAI-2K mucocutaneous and/or muscoskeletal score will be calculated in a similar manner.
 
Overall testing strategy for the pharmacodynamic endpoint
 
An optimized contrast test according to the Multiple Comparison Procedure (MCP)-Mod approach [Bretz 2005] for each considered dose-response model will be performed. The existence of dose-response effects will be tested using the maximum of the model-based contrast tests. Multiplicity adjusted p-values will be calculated using the Dunnett-distribution.
 
Pharmacodynamic endpoint analysis
 
Null and alternative hypotheses
 
The null hypothesis is that there is no dose response in terms of
 |
|--|---|

lowering of lymphocyte count ( $p$ , which is a negative value for a lowering of the lymphocyte count) from baseline to EOT, and the alternative hypothesis is the existence of a dose response:

$$H_0: p_d \geq p_{Placebo} \text{ for all doses } d = 0.5, 1, 2, 4 \text{ mg}$$

vs

$$H_1: p_d < p_{Placebo} \text{ for at least 1 dose } d = 0.5, 1, 2, 4 \text{ mg}$$

If Part B of the trial is not performed, the hypothesis will be

$$H_0: p_d \geq p_{Placebo} \text{ for all doses } d = 0.5, 1, 2 \text{ mg}$$

vs

$$H_1: p_d < p_{Placebo} \text{ for at least 1 dose } d = 0.5, 1, 2 \text{ mg}$$

To meet the objective of demonstrating existence of a dose response of ACT-334441 on the lymphocyte count reduction from baseline in subjects with SLE, the null hypotheses must be rejected by the test with a one-sided significance level of 5%.

#### Main pharmacodynamic analysis

The MCP-Mod approach consists of a set of optimized contrast tests for establishing the existence of dose-response effects. The overall strategy is described as follows:

Definition of a set of likely dose response relations (see sample size section for more details):

- Maximum effect ( $E_{max}$ ) with 50% of the maximum effect at dose 0.2 mg
- $E_{max}$  with 50% of the maximum effect at dose 0.4 mg
- $E_{max}$  with 50% of the maximum effect at dose 1.0 mg
- Quadratic with maximum effect at dose 3.0 mg (only if the 4 mg dose is studied)
- Sigmoid- $E_{max}$  with 50% of the maximum effect at dose 0.4 mg and 95% of the maximum effect at dose 2.0 mg

The existence of dose-response effects will be assessed with the optimized contrast tests. Dose-response effects are established at one sided level  $\alpha=5\%$ , if the following condition on the  $p$  value holds for at least one contrast  $i$ :  $p_i := 1 - F_{\Sigma_{Dunnett}}(Z_i) < 0.05$ , where  $F_{\Sigma_{Dunnett}}$  describes the Dunnett-distribution with

|  |   |
|--|---|
|  | 
correlation matrix <math>\Sigma_{Dunnett}</math>.
 
The model with the minimum p-value will be fitted to the data. As a sensitivity analysis, all remaining significant models will be fitted to the data and model-based dose estimates will be calculated.
 
Given established dose-response effects with MCP-Mod, PD effects will be analyzed based on pairwise comparisons of reduction in lymphocyte count from baseline for each active dose levels to placebo using an analysis of covariance (ANCOVA) model adjusted for baseline lymphocyte counts. Testing will be done with a two-sided significance level of 5%. The type-1 error will be controlled via a hierarchical ordering of the tests: pairwise comparison will be conducted in decreasing dose order.
 
The dose-response data will be summarized with point-wise and model-based estimates, standard deviation and 95% confidence intervals (CI) on the reduction in lymphocytes from baseline at the examined dose levels. A plot of the estimated dose response curve with 95% credibility interval limits will be presented along with the observed response at each dose.
 
This analysis will be performed on the PD analysis set, and a supportive analysis will be performed on the FAS and the PPS.
 
Exploratory efficacy endpoint analysis
 
The exploratory efficacy endpoint change from baseline in SLEDAI-2K score at Week 12 will be analyzed using an ANCOVA, with treatment and baseline score as factors. Missing values at Week 12 will be imputed using LOCF. The mean treatment difference including 95% CI for each ACT-334441 dose compared to placebo will be presented. A sensitivity analysis will be performed using observed data without imputation.
 
Other changes from baseline variables will be analyzed in a similar manner using an ANCOVA.
 
All exploratory efficacy endpoints will be analyzed on the FAS and PPS populations.
 |
|--|---|

|                  |  |
|------------------|--|
|                  | 
No multiplicity adjustments will be made on exploratory efficacy endpoints.
 
Safety endpoints
 
Safety endpoints will be mainly analyzed descriptively by treatment group on the Safety Set.
 
Sample size
 
The sample size for the study was determined based on simulations. A maximum % lymphocyte reduction compared to baseline of 70% was assumed based on results obtained in Phase 1 with ACT-334441 and with other S1P receptor modulators. A sample size of 64 subjects (12 in each ACT-334441 dose group of 0.5 mg, 1 mg, 2 mg, 4 mg, and 16 in the placebo group) would provide an average power of at least 90% to show a significant dose response relationship at a one-sided significance level of 5%, under the assumption of a % lymphocyte reduction compared to baseline of 0% (mean at Week 12 = <math>2.0 \times 10^9/L</math>) for placebo and a maximum of 70% for any ACT-334441 dose (mean at Week 12 = <math>0.6 \times 10^9/L</math>). The pooled SD is assumed to be <math>0.45 \times 10^9/L</math>. This takes into account 10% of subjects being excluded from the PD analysis set.
 
If Part B is not conducted and the 4 mg dose is not tested, then there will be an average power of at least 80% to show a significant dose-response relationship with three dose levels at a one-sided significance level of 5%, using the same assumptions as above (based on a total sample size of 48 subjects [12, 12, 12 and 12 in placebo, 0.5 mg, 1 mg and 2 mg, respectively]).
 
Assumptions on the placebo response rate, maximum effect sizes and candidate dose-response models are based on the observed lymphocyte count in study AC-064-101.
 |
| STUDY COMMITTEES | 
Independent Data Monitoring Committee
 
An IDMC has the overall responsibility for safeguarding the interests of subjects by monitoring data obtained in the study in an unblinded fashion and making appropriate recommendations based on the reported data, thus ensuring that the study is being conducted with the highest scientific and ethical standards. The IDMC will be fully operational prior to enrolment of the first subject into the study. The IDMC will review unblinded data at
  |

|  |   |
|--|---|
|  | 
regular intervals, will provide recommendation to apply study stopping rules (if indicated) and in addition will review interim safety data collected when all subjects enrolled into Part A have completed Visit 4 (Week 4), unless prematurely discontinued [see Section 11.5]. The composition and operation of the IDMC is described in the IDMC charter.
 
Ophthalmology Safety Board
 
An Ophthalmology Safety Board (OSB) composed of two independent ophthalmologists will review and evaluate in a blinded fashion any new or suspected case of macular edema. The composition and operation of the OSB is described in the OSB charter.
 |
|--|---|

## 15.2 Discussion and further considerations of the applied statistical methods

### 15.2.1 Clinical laboratory evaluation

**Table 16 Clinical laboratory evaluation: Marked abnormalities in laboratory parameters (adapted from Table 5 from the Clinical Study Protocol)**

| Category  | Test Code | Test Name                  | Standard Unit | Se x | LLL  | LL   | LO | HI  | HH        | HHH     |
|-----------|-----------|----------------------------|---------------|------|------|------|----|-----|-----------|---------|
| CHEMISTRY | ALB       | Albumin                    | g/L           |      | < 20 | < 30 | 35 | 52  | 71        | NA      |
| CHEMISTRY | ALP       | Alkaline Phosphatase       | U/L           | F    | NA   | NA   | 42 | 98  | > 2.5 ULN | > 5 ULN |
| CHEMISTRY | ALP       | Alkaline Phosphatase       | U/L           | M    | NA   | NA   | 53 | 129 | > 2.5 ULN | > 5 ULN |
| CHEMISTRY | ALT       | Alanine Aminotransferase   | U/L           | F    | NA   | NA   | 0  | 33  | ≥ 3 ULN   | ≥ 5 ULN |
| CHEMISTRY | ALT       | Alanine Aminotransferase   | U/L           | M    | NA   | NA   | 0  | 44  | ≥ 3 ULN   | ≥ 5 ULN |
| CHEMISTRY | AST       | Aspartate Aminotransferase | U/L           | F    | NA   | NA   | 14 | 34  | ≥ 3 ULN   | ≥ 5 ULN |
| CHEMISTRY | AST       | Aspartate Aminotransferase | U/L           | M    | NA   | NA   | 14 | 39  | ≥ 3 ULN   | ≥ 5 ULN |

| Category    | Test Code | Test Name                             | Standard Unit              | Sex | LLL    | LL    | LO   | HI   | HH                                   | HHH                              |
|-------------|-----------|---------------------------------------|----------------------------|-----|--------|-------|------|------|--------------------------------------|----------------------------------|
| CHEMISTRY   | BILI      | Bilirubin                             | umol/L                     |     | NA     | NA    | 5.1  | 20.5 | $\geq 2$ ULN                         | $\geq 5$ ULN                     |
| CHEMISTRY   | BUN       | Blood Urea Nitrogen                   | mmol/L                     |     | NA     | NA    | 3.2  | 8.2  | 20.5                                 | 41.0                             |
| CHEMISTRY   | CA        | Calcium                               | mmol/L                     |     | < 1.75 | < 2.0 | 2.15 | 2.55 | > 2.9                                | > 3.1                            |
| CHEMISTRY   | CHOL      | Cholesterol                           | mmol/L                     |     | NA     | NA    | 0    | 5.2  | > 7.75                               | > 12.92                          |
| CHEMISTRY   | CL        | Chloride                              | mmol/L                     |     | NA     | 74    | 99   | 109  | 131                                  | NA                               |
| CHEMISTRY   | CREAT     | Creatinine                            | umol/L                     | F   | NA     | NA    | 44   | 97   | > 1.5 ULN or > 1.5 $\times$ baseline | > 3 ULN or > 3 $\times$ baseline |
| CHEMISTRY   | CREAT     | Creatinine                            | umol/L                     | M   | NA     | NA    | 62   | 115  | > 1.5 ULN or > 1.5 $\times$ baseline | > 3 ULN or > 3 $\times$ baseline |
| CHEMISTRY   | GRFE      | Creatinine Clearance                  | mL/min/1.73 m  |     | <30    | <60   | 60   | NA.  | NA                                   | NA                               |
| CHEMISTRY   | GLUC      | Glucose                               | mmol/L                     |     | < 2.2  | < 3.0 | 3.3  | 5.5  | > 8.9                                | > 13.9                           |
| CHEMISTRY   | K         | Potassium                             | mmol/L                     |     | < 3.0  | < 3.2 | 3.5  | 5.1  | > 5.5                                | > 6.0                            |
| CHEMISTRY   | LDH       | Lactate Dehydrogenase                 | U/L                        |     | NA     | NA    | 120  | 246  | >=524                                | NA                               |
| CHEMISTRY   | PROT      | Protein                               | g/L                        |     | NA     | 39    | 64   | 83   | 101                                  | NA                               |
| CHEMISTRY   | SODIUM    | Sodium                                | mmol/L                     |     | < 130  | NA    | 136  | 145  | > 150                                | > 155                            |
| CHEMISTRY   | TRIG      | Triglycerides                         | mmol/L                     |     | NA     | NA    | 0    | 1.68 | > 3.42                               | > 11.4                           |
| CHEMISTRY   | URATE     | Urate                                 | umol/L                     | F   | NA     | NA    | 137  | 393  | > 590                                | > 720                            |
| CHEMISTRY   | URATE     | Urate                                 | umol/L                     | M   | NA     | NA    | 262  | 452  | > 590                                | > 720                            |
| COAGULATION | APTT      | Activated Partial Thromboplastin Time | sec                        |     | NA     | 14.0  | 24   | 37   | > 1.5 - 2.5 $\times$ ULN             | > 2.5 $\times$ ULN               |

| Category    | Test Code | Test Name                          | Standard Unit | Se x | LLL  | LL  | LO     | HI     | HH   | HHH  |
|-------------|-----------|------------------------------------|---------------|------|--|---|--------|--------|--|--|
| COAGULATION | FIBRINO   | Fibrinogen                         | g/L           |      | < 0.25 LLN or < 75% decrease from baseline or absolute value < 0.5 | < 0.75 - 0.5 LLN or 25 - < 50% decrease from baseline | 2.1    | 4.7    | 6.0  | NA   |
| COAGULATION | INR       | Prothrombin Intl. Normalized Ratio | Fraction of 1 |      | NA   | NA  | 0.8    | 1 2    | $\geq 1.5$ ULN   | $\geq 2.5$ ULN   |
| COAGULATION | PT        | Prothrombin Time                   | sec           |      | NA   | NA  | 9.4    | 13     | NA   | 100.1  |
| HEMATOLOGY  | EOS       | Eosinophils                        | 10e9/L        |      | NA   | NA  | 0      | 0 5    | > 5.0  | ND   |
| HEMATOLOGY  | HCT       | Hematocrit                         | L/L           | F    | < 20   | < 28  | 0.36 4 | 0.48 9 | > 55   | > 65   |
| HEMATOLOGY  | HCT       | Hematocrit                         | L/L           | M    | < 20   | < 32  | 0.41 6 | 0 54 1 | > 60   | > 65   |
| HEMATOLOGY  | HGB       | Hemoglobin                         | g/L           | F    | < 80 g/L   | < 100 g/L   | 115    | 160    | Increases in > 20 g/L above ULN or Increases in > 20 g/L above baseline (if baseline is above ULN) | Increases in > 40 g/L above ULN or Increases in >40g/L above baseline (if baseline is above ULN) |

| Category   | Test Code | Test Name          | Standard Unit | Sex | LLL    | LL    | LO   | HI   | HH   | HHH   |
|------------|-----------|--------------------|---------------|-----|--------|-------|------|------|--|---|
| HEMATOLOGY | HGB       | Hemoglobin         | g/L           | M   | < 80   | < 100 | 130  | 175  | Increases in > 20 g/L above ULN or Increases in > 20 g/L above baseline (if baseline is above ULN) | Increases in > 40 g/L above ULN or Increases in > above baseline (if baseline is above ULN) |
| HEMATOLOGY | NEUT      | Neutrophils        | 10e9/L        |     | < 1.0  | < 1.5 | 1.8  | 7.7  | 15.4   | NA  |
| HEMATOLOGY | PLAT      | Platelets          | 10e9/L        |     | < 50.0 | < 75  | 130  | 400  | > 600  | > 999   |
| HEMATOLOGY | RBC       | Erythrocytes       | 10e12/L       |     | NA     | NA    | 3.8  | 5.2  | NA   | NA  |
| HEMATOLOGY | RBC       | Erythrocytes       | 10e12/L       | M   | NA     | NA    | 4.5  | 5.9  | NA   | NA  |
| HEMATOLOGY | WBC       | Leukocytes         | 10e9/L        | F   | < 1.9  | NA    | 4.5  | 11.0 | > 20.0   | > 100.0   |
| HEMATOLOGY | LYM       | Lymphocytes        | 10e9/L        |     | < 0.2  | NA    | 1.00 | 4.80 | > 4.0  | ≥ 8   |
| URINALYSIS | PROT      | Protein            | mg/L          |     | NA     | NA    | 10   | 140  | 1000   | 3500  |
| URINALYSIS | PROTCR T  | Protein/Creatinine | g/mol         |     | NA     | NA    | 1.1  | 12.1 | >100   | >300  |
| URINALYSIS | PROTCR T  | Protein/Creatinine | g/mol         |     | NA     | NA    | 1.7  | 7.7  | >100   | >300  |

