### Laboratory abnormalities

Laboratory values below or above the normal range will be graded at three levels (H, HH, HHH for values above normal range and L, LL, LLL for values below the normal range) where L stands for "low", H for "high".

The term "marked abnormality" describes laboratory values above or below the thresholds, with grading of abnormalities at two levels: LL/HH and LLL/HHH. These thresholds have been defined by the sponsor in order to flag and/or communicate abnormal laboratory results from the central laboratory to the investigators, and for the purpose of standardized data analysis and reporting by the sponsor. The definitions of marked abnormal values are based mainly on the Common Terminology Criteria for Adverse Events (CTCAE) grading system (2010 v4.03) and, in specific cases (e.g., lymphocyte levels), are adjusted based on the known PD effect of the study drugs (e.g., LLL threshold for lymphocytes) [CTCAE 2010].

The term ALERT here corresponds to protocol-defined test result threshold requiring an action from the investigator as described in the protocol (e.g., repeat the test; interrupt or discontinue the study drug) and should not be confused with the term "call alert" used by the central laboratory for laboratory results, which will be communicated to the investigator. Not all ALERTS listed in this table will be "call alerts" from the central laboratory and vice versa.

PLEASE NOTE: Thresholds for abnormality of level L or H are not provided in this appendix but will be provided in the laboratory manual. Parameters for which no threshold is defined in [Table 5](#) below may be defined in the central laboratory manual.

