**Table 5**      **Thresholds for marked laboratory abnormalities for ACT-334441**

Parameter	LL	LLL	HH	HHH
Hemoglobin	< 100 g/L (< 10g/dL; < 6.2 mmol/L)	< 80 g/L (<8g/dL; < 4.9 mmol/L)	Increase in > 20 g/L above ULN or above baseline (if baseline is above ULN)	Increase in > 40 g/L above ULN or above baseline (if baseline is above ULN)
MCH	ND	ND	ND	ND
MCV	ND	ND	ND	ND
MCHC	ND	ND	ND	ND
Hematocrit	< 28% (female) < 32% (male)	< 20%	> 60% (male) > 55% (female)	> 65%
Platelet count	< 75 × 10 e9 /L (< 75,000/mm  )	< 50.0 × 10 e9 /L (<50,000/mm  )	> 600 × 10 e9 /L	> 999 × 10 e9 /L
RBC count	ND	ND	ND	ND
WBC count	ND	< 1.9 × 10 e9 /L	> 20.0 × 10 e9 /L (>20 000/mm  )	CTCAE (grade 3) > 100.0 × 10 e9 /L (>100 000/mm  )
Lymphocyte	ND	< 0.2 × 10 e9 /L (< 200/mm  ) ALERT* < 0.2 × 10 e9 /L (< 200/mm  )	> 4.0 × 10 e9 /L (> 4000/mm  )	≥ 8 × 10 e9 /L (> 8000/mm  )
Neutrophils	< 1.5 × 10 e9 /L (< 1,500/mm  )	< 1.0 × 10 e9 /L (< 1000/mm  )	ND	ND
Eosinophils	ND	ND	> 5.0 × 10 e9 /L or > 5% (> 5000 cells/mm  )	ND
Monocytes	ND	ND	ND	ND
Basophils	ND	ND	ND	ND
Polymorphonuclear leucocyte/Band cells	ND	ND	> 90%	> 95%
AST	ND	ND	≥ 3 ULN (U/L) ALERT ≥ 3 ULN	≥ 5 ULN (U/L) ALERT ≥ 5 ULN ≥ 8 ULN
ALT	ND	ND	≥ 3 ULN (U/L) ALERT ≥ 3 ULN	≥ 5 ULN (U/L) ALERT ≥ 5 ULN ≥ 8 ULN
Total bilirubin	ND	ND	≥ 2 ULN (umol/L) ALERT ≥ 2 ULN combined with ALT or AST ≥ 3 ULN	≥ 5 ULN (umol/L)
Alkaline Phosphatase	ND	ND	> 2.5 ULN (U/L)	> 5 ULN (U/L)

Confidential

INR	ND	ND	≥ 1.5 ULN** or ≥ 1.5 times above baseline if on anticoagulation ALERT ≥ 1.5 combined with ALT or AST ≥ 3 ULN	≥ 2.5 ULN** or ≥ 2.5 times above baseline if on anticoagulation
Activated partial thromboplastin time prolonged (aPTT)	ND	ND	> 1.5 - 2.5 × ULN	> 2.5 × ULN
Lactate dehydrogenase	ND	ND	ND	ND
Creatinine	ND	ND	> 1.5 ULN (umol/L) or > 1.5 × baseline	> 3 ULN (umol/L) or > 3 × baseline
Creatinine Clearance (eGFR)	<60 ml/min/1.73m 	<30 ml/min/1.73m 	ND	ND
Urea	ND	ND	> 2.5 ULN (mmol/L)	> 5 ULN (mmol/L)
Uric acid	ND	ND	> 0.59 mmol/L (>10 mg/dL)	> 0.72 mmol/L (>12 mg/dL)
Proteinuria	ND	ND	≥1.0 g/24h	≥3.5 g/24h
Protein/creatinine ratio	ND	ND	>100 mg/mmol***	>300 mg/mmol***

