### 5.8.10 Laboratory

Laboratory test results are transferred from the central laboratory or, if assayed locally, entered in local laboratory eCRF. Assessments are performed at each scheduled visit from Visit 1 (Screening) to Visit 7 (EOS), and at unscheduled visits if required.

The following parameters are assayed:

- **Hematology:** Hemoglobin, hematocrit, platelets, MCH, MCV, MCHC, reticulocytes/erythrocytes, erythrocytes, leukocytes count with differential count (basophils, eosinophils, lymphocytes, neutrophils, monocytes, and basophils/ leukocytes, eosinophils/ leukocytes, lymphocytes/ leukocytes, monocytes/ leukocytes, neutrophils/ leukocytes);
- **Blood chemistry:** Aspartate aminotransferase (AST), alanine aminotransferase (ALT), alkaline phosphatase, total bilirubin (TBL), direct bilirubin, lactate dehydrogenase, creatinine, blood urea nitrogen, urate, glucose, cholesterol, triglycerides, sodium, potassium, chloride, calcium, protein, albumin, creatinine clearance;
- **Coagulation tests:** prothrombin time, INR, activated partial thromboplastin time;
- **Urine protein-to-creatinine ratio** (Visits 1, 2 and 6): Creatinine, protein, protein/ creatinine.

For women of childbearing potential, serum pregnancy tests are performed at Visit 1 (Screening) and Visit 7 (EOS) (central laboratory), and urinary pregnancy tests are performed at all other visits and collected in the dedicated eCRF page.

Urine dipsticks are used to perform the urinalysis at all visits (e.g., pH, glucose, proteins, blood, leukocytes) and the results are recorded in the dedicated eCRF page.

The following endpoints are defined:

- Absolute value and absolute change from baseline in laboratory parameters (hematology, blood chemistry, and urinalysis) at each post-baseline analysis visit up to EOS;
- Treatment-emergent laboratory test abnormalities based on reference ranges (central laboratory) and abnormality thresholds (as defined in appendix 7 of the study protocol and in Section 15.2).

For these abnormalities, additional criteria are defined to characterize the occurrence of treatment-emergent abnormalities during the treatment period in each direction separately (low and high).

Treatment-emergent liver function abnormalities occurring at any time post-baseline are identified according to the following criteria, where a subject is considered to have met the criteria if they have at least one abnormality based on the worst post-baseline value measured (up to EOS):

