#### 10.9.4 Laboratory tests

Descriptive summary statistics by analysis visit and treatment group are provided for observed values and absolute changes from baseline by category (hematology/ coagulation, chemistry, urinalysis). Data are displayed in SI units as provided by the central laboratory.

Values from local labs are not included in the different summaries but are included in the listings.

For categorical urinalysis parameters (dipstick), qualitative descriptive statistics for recorded values are presented by parameter and visit.

Treatment-emergent laboratory abnormalities are summarized by lab category, parameter and severity over the study treatment period. For each parameter, the severity is based on the position of the value against reference ranges (central laboratory) and additional thresholds for significance (see appendix 7 of the study protocol) and the worst abnormality is considered in each direction separately (Low and High). In addition, for the liver tests, the number and percentages of subjects with values above the normal ranges, or with abnormal values that are of a certain size (e.g., twice the upper limit of the normal ranges; see section 5.1.10.5, figure 3 of the study protocol) are presented along with their 95% Clopper-Pearson confidence intervals. For each parameter, the maximum highest value recorded during the treatment period is taken into account.

The denominator for percentages is the number of subjects with at least one post-baseline assessment.

All data are presented in the listings:

- hematology, chemistry, coagulation, urinalysis
- urinary dipstick
- viral serology (if assay is required)/ tuberculosis test results are listed along with the other baseline characteristics

- serum and urinary pregnancy tests results are listed along with the childbearing potential information

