## 11.2 Analysis variables

### 11.2.1 General

**Baseline value** is defined as the last non-missing value before date and time of first dose intake of double-blind treatment.

**Analysis value** is defined as the value at the visit (numeric result in standard units).

**Absolute change from baseline** is defined as post-baseline value minus baseline value, i.e., a positive sign indicates an increase as compared to baseline.

**Percent change from baseline** is defined as the absolute change from baseline divided by the baseline value (if the baseline value is  $> 0$ ) and then multiplied by 100.

**Ratio to baseline** is defined as the value at the visit divided by the value at baseline (if the baseline value is  $> 0$ ).

**Analysis Date** is defined as the numeric SAS date derived from the Date/Time of assessment. It can be an imputed date [cf. section 12 for more details].

**Analysis Start Date** is defined as the numeric SAS date derived from the Start Date/Time of an event. It can be an imputed date [cf. section 12 for more details].

**Analysis End Date** is defined as the numeric SAS date derived from the End Date/Time of an event. It can be an imputed date [cf. section 12 for more details].

**Analysis End Relative Day** is estimated for several assessments, including AE end, treatment interruptions, concomitant medication end. It refers to the number of days between the end of the specific event and the first study treatment intake.

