For the parameters assayed as a categorical variable (e.g., Protein), the analysis value is defined only as a character value.

**Analysis Reference Range Indicator** is derived to identify marked abnormalities according the Adapted table 5 from the study protocol [included in Section 15]. It is only defined for results coming from the central laboratory, it is based on the normal range indicator provided by ACM (L, LL, H, HH) and augmented or modified according to the adapted table 5.

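### SAP Table 16 grades hematocrit in L/L with protocol Table 5's percent cut-offs left unconverted, so its LLL and HHH grades fail if programmed as written

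*SAP*

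**What the plan says.** Protocol Appendix 7 defines marked laboratory abnormalities "with grading of abnormalities at two levels: LL/HH and LLL/HHH". Its Table 5 states the hematocrit thresholds in percent. The LL cell, for example, reads "< 28% (female) < 32% (male"), and the other cells are < 20% for LLL, > 55% (women) or > 60% (men) for HH, and > 65% for HHH.

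SAP Table 16 presents itself as an adaptation of that table. It lists hematocrit with standard unit L/L and adds the laboratory's normal limits as fractions. The row for women is "< 20 | < 28 | 0.36 4 | 0.48 9 | > 55 | > 65"; the spaces inside the limits come from text extraction, and they read 0.364 and 0.489. The row for men has < 20, < 32, 0.416, 0.541, > 60 and > 65.

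Three SAP sections say how thresholds are applied, and they do not point to one source:

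- Section 5.8.10 defines treatment-emergent abnormalities by reference ranges and thresholds "as defined in appendix 7 of the study protocol and in Section 15.2", so it cites both tables.
- Section 10.9.4 grades severity by reference ranges and "additional thresholds for significance (see appendix 7 of the study protocol"), so it cites the protocol table only.
- Section 11.2.15 derives the analysis reference range indicator "based on the normal range indicator provided by ACM (L, LL, H, HH) and augmented or modified according to the adapted table 5", so it starts from the laboratory's flags and then applies SAP Table 16.

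Section 11.2.1 fixes the scale on which values are compared: the analysis value "is defined as the value at the visit (numeric result in standard units"), which for hematocrit is L/L.

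**The concern.** Within one row, the normal limits are on a 0-to-1 scale and the marked cut-offs are on a 0-to-100 scale. The worst low grade then applies to any hematocrit, including the table's own limits of normal, and the two high grades apply to none. Nothing in the SAP tells the programmer to multiply hematocrit by 100 before grading.

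The output at risk is in Section 10.9.4: "Treatment-emergent laboratory abnormalities are summarized by lab category, parameter and severity over the study treatment period", with the worst grade taken separately in the low and high directions. Safety is a main objective, and treatment-emergent laboratory abnormalities are a listed safety endpoint. If Table 16 is programmed literally, the hematocrit row cannot separate mild from marked low values and can never show HHH.

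**Working it through.** **Inputs.** Thresholds in percent come from protocol Appendix 7, Table 5. The unit, normal limits and thresholds as adapted come from SAP Table 16. The scale of the analysis value is in SAP 11.2.1.

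**Conversion.** L/L = percent / 100.

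| Grade | Protocol Table 5 | SAP Table 16 as written, unit L/L | Table 5 / 100 |
|---|---|---|---|
| LLL | < 20% | < 20 | < 0.20 |
| LL | < 28% F, < 32% M | < 28 F, < 32 M | < 0.28 F, < 0.32 M |
| HH | > 55% F, > 60% M | > 55 F, > 60 M | > 0.55 F, > 0.60 M |
| HHH | > 65% | > 65 | > 0.65 |

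**Range check.** A volume fraction lies between 0 and 1. So < 20, < 28 and < 32 are always true, and > 55, > 60 and > 65 are never true. Against the highest normal limit in the table, 20 / 0.541 = 37, so the LLL cut-off is about 37 times that limit. On a grid from 0 to 1 in steps of 0.001, 100% of values meet LLL and 0% meet HH or HHH, for both sexes.

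**Order check.** Read from LLL to HHH, a row should increase. As written, the row for women runs 20, 28, 0.364, 0.489, 55, 65. After division by 100 it runs 0.20 < 0.28 < 0.364 < 0.489 < 0.55 < 0.65, and the row for men runs 0.20 < 0.32 < 0.416 < 0.541 < 0.60 < 0.65. Both then increase throughout.

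**Is it a missed conversion?** Other Table 16 rows were converted. Urate is 0.59 mmol/L x 1000 = 590 umol/L, and the fibrinogen absolute limit is 50 mg/dL = 0.5 g/L. Percent signs survive elsewhere in Table 16, so their loss here is unlikely to come from text extraction.

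**Grades under three readings.** (a) uses protocol Table 5. (b) starts from the laboratory's L/LL/H/HH flags and applies Table 16 to the out-of-range values. (c) uses the Table 16 thresholds alone and is shown for its low-direction grade.

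| Value (L/L) | (a) | (b) | (c) |
|---|---|---|---|
| F 0.19 | LLL | LLL | LLL |
| F 0.25 | LL | LLL | LLL |
| F 0.36 | L | LLL | LLL |
| F 0.40 | normal | normal | LLL |
| F 0.58 | HH | H, or laboratory HH | LLL |
| F 0.66 | HHH | H, or laboratory HH | LLL |
| M 0.30 | LL | LLL | LLL |
| M 0.40 | L | LLL | LLL |
| M 0.66 | HHH | H, or laboratory HH | LLL |

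Under (b), the values that can be over-graded are 0.20 to < 0.364 in women and 0.20 to < 0.416 in men. Their proper grade is LL (0.20 to < 0.28 F, 0.20 to < 0.32 M) or L (0.28 to < 0.364 F, 0.32 to < 0.416 M). Under (c), the high direction also stops at H.

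**Can low values occur?** Yes. Exclusion criterion 31 removes only subjects with hemoglobin below 9 g/dL, which is 90 g/L. Table 16's lower limits of normal for hemoglobin are 115 g/L (F) and 130 g/L (M), so anemic subjects can enter.

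**The case against.** The best counter-argument is that the intended thresholds are not in doubt. Section 10.9.4, which specifies the severity summary, names only protocol Appendix 7, where the percentages are intact, and Table 16 says it is adapted from that table. A programmer following 10.9.4 and comparing like units would misgrade nothing. The slip also reveals itself, since < 28 stands next to a lower limit of 0.364.

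It can further be said that reading (b) is not fully specified. Section 11.2.15 gives no algorithm for augmenting or modifying the laboratory's flags. Protocol Appendix 7 describes the marked thresholds as serving to flag central-laboratory results, and protocol Section 5.1.10.2 mentions counts flagged LLL, so the laboratory may itself supply LLL and HHH. The laboratory manual is not available to settle this. Reading (c) sits badly with 11.2.15, where the laboratory flags come first.

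Much of this stands, and it is why the consequence has to be stated conditionally. It does not remove the error. Section 11.2.15 is the derivation text. It lists only L, LL, H and HH as laboratory flags and assigns marked abnormalities by Table 16. Section 5.8.10 cites both tables, which now disagree for hematocrit. A pre-specified threshold should not depend on an undocumented correction by the programmer.

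**Conclusion.** The concern holds. All eight marked hematocrit cut-offs in SAP Table 16, four grades for each sex, are off by a factor of 100 against the unit stated in the same row, and they conflict with protocol Table 5.

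The size of the effect depends on the text followed. Under protocol Appendix 7, no value is misgraded. Under Section 11.2.15, assuming the laboratory supplies only the four flags listed there and Table 16 may override them, any below-range value can become LLL and HHH is unreachable, although a laboratory HH may survive. Under Table 16 alone, every value is LLL. The documents give no hematocrit distribution, so the number of subjects affected cannot be stated.

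The reach is narrow: one row of a descriptive table. The main pharmacodynamic analysis, the by-visit laboratory summaries, the listed values and the hemoglobin grading, whose units are right, are unaffected. It is a definite error that should be corrected, but no main conclusion of the trial turns on it.

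**What to change.** In SAP Table 16, restate the hematocrit cut-offs in L/L:

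- Women: LLL < 0.20, LL < 0.28, HH > 0.55, HHH > 0.65.
- Men: LLL < 0.20, LL < 0.32, HH > 0.60, HHH > 0.65.

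These are protocol Table 5's own values in the SAP's stated unit, so no new threshold is introduced and the two sources cited in Section 5.8.10 then agree. The cost is eight cells in the SAP, edited before the laboratory abnormality tables are run. The protocol needs no amendment, because its table already carries the percent signs.
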